## **10.8. Procedure(s) to Account for Missing or Spurious Data**

Missing data will be omitted from the analyses. The group sizes are too small to consider multiple imputations.

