**Secondary outcomes:**

- Participant adherence to dietary intervention (achieving dietary AGE intake <8000 kilounits [kU]/day).
- Slope of SAF values over 6 months.
- Change in SAF values at 6 months.
- Change in weight over 6 months.
- Change in aortic pulse wave velocity (aPWV).
- Change in high-sensitive C reactive protein (hsCRP).
- Change in quality of life.

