#### **Low AGE diet (intervention group)**

The low AGE diet will be the same as the standard diet in terms of calories (i.e. 30-35 kcal/kg/day) and protein (0.75-0.84 g/kg/day). However, it will reduce the dietary AGE content by changing cooking methods in food preparation to avoid exposure to dry heat such as frying, broiling, grilling and roasting, and to favour cooking with lower temperatures and high-water content as in stewing, steaming, boiling and poaching. In addition, the low-AGE group will be instructed to choose foods with low content of AGEs based on a food choice list that will contain examples of foods commonly available in the UK to be chosen as "allowed," "moderate intake," or "occasional." The goal will be to reduce dietary AGE intake to less than 8000 kU/day.

Dietary advice will be provided in person by an investigator with training and previous experience as a dietitian. Adherence to diets will be evaluated by means of a 3-day food diary (2 weekdays and 1 weekend day) every month. Monthly forms and written instructions on how to complete the 3-day food diaries will be sent by post to the participants. We will ask participants to return the completed food diaries in a pre-paid envelope. If needed, supplementary relevant diet information will be obtained by telephone consultation once the food diaries have been recorded and returned to the research dietitian.

There will be a follow-up meeting or discussion by telephone with participants randomised to the intervention group after 2 weeks of starting the study in order to reinforce the adherence and understanding of the intervention.

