## 7.6. Withdrawal Criteria

Participants will be withdrawn from the study if they withdraw their consent at any point or decline to comply with the dietetic intervention or develop malnutrition. Female participants will be withdrawn from the study if they become pregnant.

Participants may be withdrawn from the study either at their own request or at the discretion of the Investigator. The participants will be made aware that this will not affect their future care. Participants will be made aware (via the information sheet and consent form) that should they withdraw the data collected to date cannot be erased and will be used in the final analysis.

If participants fail to attend for their study visits, a member of the research team will try to contact them by telephone within 24 hours of their appointment and by written correspondence within a week of the missed appointment. Multiple attempts at contact will be made by the research team over a period of a month before stating that a participant has been lost to follow-up.

Data that is collected prior to withdrawal will be kept and analysed as part of the data set. The date, time and reason for participant withdrawal will be documented on the case report form (CRF).

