#### **10.3.2. Outcome Analysis**

Summary measures of all baseline variables will be calculated and reported. Primary and secondary outcomes will be compared between the two groups (Low AGE Diet vs. Standard Diet) at 6 months using a t-test if data are normally distributed or a Mann Whitney U test if not. Analysis will be by intention to treat.

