#### **10.7. Analysis Groups**

The two groups for analysis will be the Low AGE diet and Standard diet groups. Analyses will be by intention to treat and will include all participants who were randomised and received at least one session of dietary counselling regarding their diet (all-treated population).

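### Participants withdrawn for declining the diet drop out of the 6-month adherence rate, although they are known to be non-adherent

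*Combined protocol and SAP*

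**What the plan says.** Section 3.1 lists fidelity and adherence among the questions the feasibility study must answer. Section 3.2 makes adherence a yes/no secondary outcome: "Participant adherence to dietary intervention (achieving dietary AGE intake <8000 kilounits [kU]/day". It gives no denominator, time point or instrument.

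The other relevant provisions are:

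- **Time point (10.3.2):** "Primary and secondary outcomes will be compared between the two groups (Low AGE Diet vs. Standard Diet) at 6 months".
- **Withdrawal (7.6):** the grounds include participants who "decline to comply with the dietetic intervention or develop malnutrition". Pregnancy, withdrawal of consent and investigator discretion are also grounds. On earlier data: "Data that is collected prior to withdrawal will be kept and analysed as part of the data set".
- **Missing data (10.8):** "Missing data will be omitted from the analyses". No outcome is excepted. Multiple imputation is ruled out because the groups are small.
- **Analysis set (10.7):** called intention to treat, but limited to those "randomised and received at least one session of dietary counselling regarding their diet (all-treated population".
- **Instrument:** section 7.3 says "Adherence to diets will be evaluated by means of a 3-day food diary (2 weekdays and 1 weekend day) every month", returned by post: "We will ask participants to return the completed food diaries in a pre-paid envelope". Section 7.4 uses the diary for energy, fat and protein, and a food frequency questionnaire for dietary AGE intake at baseline, 3 and 6 months.

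**The concern.** For most outcomes a missing value is simply unknown. For adherence, the reason a value is missing can itself be the answer. A participant withdrawn for declining the diet is as clear a case of non-adherence as the trial can record, yet under the omission rule that person is not counted as a failure. They leave both numerator and denominator.

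A definitive trial would use this figure to judge whether the diet can be delivered and how far to discount the expected effect. A rate among those who stayed and supplied intake data answers a narrower question than the rate among those allocated to the diet. Section 13.1 plans a grant application for a larger trial if this study succeeds, so the adherence figure has a direct use.

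**Working it through.** **The plan's own figure.** Section 10.1 gives SD 0.64 AU, difference 0.6 AU, alpha 0.05 (sidedness not stated; two-sided assumed) and 80% power. Per group, n = 2 × (1.960 + 0.842)² × 0.64² / 0.6² = 17.9, so 18. Allowing 10% drop-out, 18/0.9 = 20 per arm and 40 in total. This reproduces the plan and fixes two inputs: 20 allocated to the low-AGE diet, and 2 of them lost at the planned rate. The plan states no expected adherence rate, so the counts below are assumptions.

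**Participants withdrawn for declining the diet.** Let x be the number on target and m the number so withdrawn. The omission rule gives x/(20 − m). Counting the m as what they are known to be gives x/20. The first is larger whenever x and m are both above zero, and the ratio is 1/(1 − d) with d = m/20.

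| Allocated | On target | Missing | Omitted | Missing counted as non-adherent | Difference (points) | Ratio |
|---|---|---|---|---|---|---|
| 20 | 12 | 2 | 12/18 = 66.7% | 12/20 = 60.0% | 6.7 | 1.11 |
| 20 | 12 | 4 | 12/16 = 75.0% | 12/20 = 60.0% | 15.0 | 1.25 |

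**Sampling error.** Wilson 95% intervals are 43.7 to 83.7% for 12/18, 50.5 to 89.8% for 12/16 and 38.7 to 78.1% for 12/20. A 6.7-point shift is well inside the first interval.

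**Other missing records.** Let p_obs be the rate among those with data and q the rate among the missing. The rate in everyone is (1 − d) × p_obs + d × q, so the bias of the available-case rate is d × (p_obs − q). With p_obs = 75% and d = 20%:

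| q | Bias (points) |
|---|---|
| 0% | +15 |
| 25% | +10 |
| 50% | +5 |
| 75% | 0 |
| 100% | −5 |

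The bias is upward only if the missing adhere less than those observed.

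**Both kinds together.** Suppose 12 are on target and 4 have no value: 2 declined the diet and 2 are missing for other reasons. Counting the 2 decliners as non-adherent, the lower bound is 12/20 = 60% and the upper bound is (12 + 2)/20 = 70%. The available-case rate, 12/16 = 75%, lies above both.

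**The case against.** **Omission is only one reading.** Section 7.6 records the date and reason of withdrawal and keeps earlier data, section 7.5 schedules adherence monthly, and section 10.7 keeps everyone counselled at least once. An analyst could treat a recorded decliner as having a known status. That is fair, and it is why a definition is needed. But no section says to do it. No rule carries an earlier diary into the 6-month outcome, and the intention-to-treat label does not supply a value that section 10.8 then omits.

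**Is the whole rate inflated by construction?** A reader might infer this, but the documents do not support it. Participants withdrawn for malnutrition or pregnancy may have been adherent, and so may those who fail to return a record. For them the bias can be zero or negative.

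**Are all who miss the target withdrawn?** This is also tempting, and also unsupported. Section 7.6 covers those who decline to comply. Someone who tries the diet and exceeds 8000 kU/day stays in, and counts as non-adherent if intake is recorded.

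**Losses will be visible.** The CONSORT diagram in section 10.3.1 shows losses and exclusions from analysis by arm, with reasons, so a careful reader might rebuild the fuller denominator. This reduces the harm but does not set the reported rate. The plan also contains no adherence threshold for progression, so no specific decision can be said to turn on the bias.

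**Postal return affects diaries only.** This stands. That lapsed participants return fewer diaries is plausible but is an assumption.

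**Conclusion.** The concern holds in a limited form. Sections 7.6, 10.3.2 and 10.8 together leave participants withdrawn for declining the diet out of the 6-month adherence rate, and for that group the bias is certainly upward. For all other missing intake records the direction is not known in advance.

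The overstatement is about 7 points at the plan's 10% loss and 15 points at twice that loss. Both figures assume 12 of 20 on target and that everyone missing is non-adherent. At 10% loss this is modest beside the sampling error. A confidence interval reflects sampling error, however, and does not reveal this shift. Because adherence is a named feasibility objective, the definition should be settled before analysis.

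**What to change.** Exempt the adherence outcome from the omission rule in section 10.8, and define it in section 3.2 or 10.8 as follows:

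1. Adherence is intake below 8000 kU/day at 6 months. Name the instrument, since section 7.3 points to the diary and section 7.4 to the questionnaire.
2. The denominator is everyone randomised to the low-AGE diet. State that this differs from the all-treated set in section 10.7.
3. Those who stopped the diet, or were withdrawn for declining it, count as not adherent.
4. For those missing for any other reason, report the rate with them counted as not adherent (lower bound) and as adherent (upper bound).
5. Show the available-case rate beside these bounds.

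The clinical withdrawal rule is left unchanged. The cost is a few lines of text and no new data or visits. The headline figure will be less favourable, and the lower bound may class some adherent participants as non-adherent. The upper bound and the available-case rate show how much that could matter.

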## **11. MONITORING, AUDIT & INSPECTION**

The Investigator(s) must ensure that source documents and other documentation for this study are made available to study monitors, the REC or regulatory authority inspectors. Authorised representatives of the Sponsor may visit the participating sites to conduct audits/inspections.

Monitoring and source data verification will be conducted by the Sponsor according to their requirements, based on the risk assessment of the study. As a low-risk study, routine monitoring is not expected but may be conducted on an ad-hoc bases. The study may be audited by the Sponsor at any time, according to the Sponsor's audit programme.

## **12. ETHICAL AND REGULATORY CONSIDERATIONS**

### **12.1. Assessment and Management of Risk**

The Sponsor has conducted the necessary risk assessment for this study and determined it as a low-risk study.

### **12.2. Peer review**

This study has been peer reviewed as part of the British Renal Society and Kidney Care UK Research Grant application process.

### **12.3. Public and Patient Involvement**

The Centre for Kidney Research and Innovation (CKRI) at UHDB NHS Foundation Trust has an established patient focus group that meets regularly to discuss all research projects and activities. This proposal was discussed at that meeting; the group felt that this was an interesting and important area to study; many gave their own anecdotes of their own and fellow patients experience of heart problems causing ill health and death. In addition, this project has been discussed with the more than 20 kidney transplant patients who participated in my MSc; these are the patients who have pushed for continued research in this area as they recognise the potential benefits for themselves and their fellow kidney transplant recipients. The focus group has agreed to review and feedback on this project, in addition to reviewing the study documentation and dissemination of its findings.

A member of the CKRI focus group is an advocate of co-production with both clinical staff and patients having an equal voice working together to create something new that meets everyone's needs and improves the lives of those who are affected by kidney disease and believes that utilizing this approach for this project will maximize its impact. [name] is especially supportive of this project

as he believes this is a novel research area that has potentially wide-ranging benefits for people affected by kidney disease and both the transplant and renal communities.

[name] is an academic with experience of research design including both qualitative and quantitative methodology and skills in academic writing. He is also under the care of the renal team at UHDB and as such has a specific interest in this research design. [name] was involved in the development of this application and will provide ongoing support in:

- Writing the plain English summary.
- Reviewing the study documentation (e.g. the PIS) and study processes (e.g. Recruitment strategies).
- Reviewing the appropriateness of the outcome measures.
- Contribute to the development of the intervention.
- Contribute to the development of the semi-structured interview.
- Will be involved in the analysis of the qualitative interviews by acting as a third coder.
- Contribute to the dissemination of the study.
- Contribute to the development of the definitive study.

It is recognised that [name] will need to be appropriately reimbursed for his commitment and costs have been calculated in line with the INVOLVE Guidance ([www.invo.org.uk](http://www.invo.org.uk))

#### **12.4. Research Ethics Committee (REC) & Regulatory Considerations**

The study will be conducted in compliance with the approved protocol and the Declaration of Helsinki. The protocol and all related documentation (e.g. informed consent form, PIS, questionnaires) will be reviewed by a Research Ethics Committee (REC). The investigator will not begin any participant activities until approval from the HRA and REC has been obtained and documented. All documentation and correspondence must be retained in the trial master file/investigator site file. Substantial amendments that require HRA and REC (where applicable) review will not be implemented until the HRA and REC grants a favourable opinion (with the exception of those necessary to reduce immediate risk to participants).

It is the responsibility of the CI to ensure that an annual progress report (APR) is submitted to the REC within 30 days of the anniversary date on which the favourable opinion was given, annually until the study is declared ended. The CI is also responsible for notifying the REC of the end of study (see Section 6.9) within 90 days. Within one year of the end of study, the CI will submit a final report with the results, including any publications/abstracts to the REC.

Before any site can enrol a patient into the study, confirmation of capacity must be sought from the site's research and development (R&D) department. In addition, for any amendment that will potentially affect the site's permission, the research team must confirm with the site's R&D department that permission is on-going (Section 12.10).

## **12.5. Protocol Compliance**

The investigator is responsible for ensuring that the study is conducted in accordance with the procedures described in this protocol. Prospective, planned deviations and/or waivers to the protocol are not acceptable. Accidental protocol deviations may happen and as such these must be reported according to the Sponsors SOP. Deviations from the protocol which are found to frequently recur are not acceptable, will require immediate action, and could potentially be classified as a serious breach.

## **12.6. Notification of Serious Breaches to GCP and/or the Protocol**

A “serious breach” is a departure from the protocol, Sponsor procedures (i.e. SOPs), or regulatory requirements which is likely to effect to a significant degree –

- (a) The safety or physical or mental integrity of the subjects of the study; or
- (b) The scientific value of the study.

If a serious breach is identified, the investigator should notify the Sponsor immediately (i.e. within 1 working day) using the ‘Non-CTIMP Notification of a Serious Breach’ form. The report will be reviewed by the Sponsor and CI, and where appropriate, the Sponsor will notify the REC within 7 calendar days of being made aware of the breach.

## **12.7. Data Protection and Patient Confidentiality**

The study will be conducted in accordance with the Data Protection Act 2018. The investigator must ensure that participant’s anonymity is maintained throughout the study and following completion of the study. Participants will be identified on all study specific documents (except for the informed consent form and enrolment log) only by the participants study specific identifier (and initials if deemed necessary). This identifier will be recorded on documents, biological samples and the database. The Investigator Site File will hold an enrolment log detailing the study specific identifier alongside the names of all participants enrolled in the study.

All documents will be stored securely with access restricted to study staff and authorised personnel. [name] will act as the custodian of the data generated in the study.

## **12.8. Financial and Other Competing Interests for the Chief Investigator, Principal Investigators at Each Site and Committee Members for the Overall Study Management**

The CI, PI and all committee members have no conflicts of interest to declare.

## **12.9. Indemnity**

As UHDB is acting as the research Sponsor for this study, NHS indemnity applies. NHS indemnity provides cover for legal liabilities where the NHS has a duty of care. Non-negligent harm is not covered by the NHS indemnity scheme. UHDB, therefore, cannot agree in advance to pay

compensation in these circumstances. In exceptional circumstances, an ex-gratia payment may be offered.

#### **12.10. Amendments**

Changes to the protocol will be documented in written protocol amendments. The Sponsor is responsible for deciding if an amendment should be deemed substantial or non-substantial. Substantial amendments will be submitted to the relevant regulatory bodies (i.e. REC, HRA) for review and approval. The amendments will only be implemented after approval and a favourable opinion has been obtained. Non-substantial amendments will be submitted to the HRA for their approval/ acknowledgment. Amendments will not be implemented until all relevant approvals are in place.

#### **12.11. Access to Final Study Dataset**

The Chief Investigator [name] and Co – Investigators [name], [name] and [name] [name] will have access to the final dataset.

### **13. DISSEMINATION POLICY**

#### **13.1. Dissemination Policy**

The aim of this dissemination plan is to ensure the impact of the new knowledge generated is maximized.

Findings will be disseminated in the following ways:

- Abstracts will be submitted to professional conferences including nationally at UK Kidney Week and The British Transplantation Society in addition to local meetings. Internationally at The American Society of Nephrology, The European Renal Association and The European Society for Organ Transplantation.
- We will work with our organisation's communication team to share the findings of this study across the organisation and more widely.
- We will utilise social media platforms to share our findings. We have an established Renal Team and CKRI twitter account accessed by both patients and staff to support this.
- Articles will be submitted to peer review journals.
- Via social media which I believe is an underutilized resource for engagement, recruitment and dissemination.
- The success of this work will also be used to promote the non-medical clinical academic career organizationally, locally and nationally through the National Institute of Health Research 70 at 70 network which the CI is a member of.

In addition, the findings of this study will be specifically shared with patients:

- The findings of this study will be disseminated via patient groups nationally such as Kidney Care UK and locally through the Derby Kidney Patients Association and the CKRI PPI group, in addition to the annual renal showcase.

- We will work with our organisations communication team to share the findings of this study, specifically to patients linking it to our patient facing website.

If this feasibility study is successful, we will submit a grant application (Research for Patient Benefit) to fund a large randomized controlled trial.

### **13.2. Authorship Eligibility Guidelines and any Intended Use of Professional Writers**

The Chief Investigator [name] and Co – Investigators [name], [name] and [name] [name] will be granted authorship on the final study report.

## 15. APPENDICES

### 15.1. Appendix 1 – Reference values of skin autofluorescence per age group.

Age group (years)	Skin autofluorescence value (mean $\pm$ SD)
10-19	1.11 $\pm$ 0.20
20-29	1.53 $\pm$ 0.30
30-39	1.73 $\pm$ 0.42
40-49	1.81 $\pm$ 0.36
50-59	2.09 $\pm$ 0.36
60-69	2.46 $\pm$ 0.57
70-80	2.73 $\pm$ 0.55
>80	2.71 $\pm$ 0.44

Adapted from: Koetsier M, Lutgers HL, de Jonge C et al. (2010) Reference values of skin autofluorescence. *Diabetes Technol Ther* 12, 399–403.

### 15.2. Appendix 2 – Amendment History

Amendment No.	Protocol version no.	Date issued	Author(s) of changes	Details of changes made
